11.3 Secondary assessments

We will test the hypothesis that the fraction of arm A and arm B patients with at least 85% reduction in PSA at 32 weeks will be the same. We will sort the 66 patients 32 week PSAs into groups above or below their grand median 32 week PSA. We will then submit the doubly dichotomized data to Fisher's exact test. The test will distinguish an odds ratio of 3.19 from one of 1.0 with 80% power and at most 10% type I error.

We will characterize the time to PSA progression and the time to onset of metastatic disease using the method of Kaplan and Meier. We will compare arms A and B for each of these end points with log-rank tests. Patients will be followed for PSA progression and for onset of metastatic disease for at least 60 months.

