1.2 Androgen receptor role in prostate cancer

Several studies demonstrated that the androgen receptor (AR) plays a crucial role in pathogenesis of prostate cancer¹⁸ and its progression in castration resistant disease¹⁹. AR is a member of the steroid receptor super family and controls expression of several genes involved in cell survival, differentiation, proliferation, and metabolism²⁰. AR activation and overexpression are consistent findings in castration resistant clones, demonstrating the pivotal role of this molecular pathway²¹. The regulation of AR activation can be initiated by ligand-dependent and ligand-independent mechanisms²².

Ligand-dependent activation is the predominant pathway in normal and castration sensitive prostate cancer cells. In the castrate environment it is sustained in part by overexpression and mutations of AR that exploit multiple mechanisms²³ including AR hypersensitivity to very low intracellular levels of androgens²⁴ and promiscuity for binding other steroid hormones (such as progesterone and estradiol)²⁵. In addition, prostate cancer cells develop ligand independent mechanisms to synthesize their own androgens by increasing the expression of genes that convert adrenal androgens to testosterone²⁶. Therefore, both pathways of AR activation remain activated in castration-resistant disease.

Antiandrogens regulate AR function by competing for agonists binding to the AR, by decreasing AR phosphorylation by various growth factors²⁷ and by preventing recruitment co-activators to initiate transcription of target downstream genes²⁸. In the clinic, antiandrogens, such as bicalutamide, have been used in non-castrate and castration resistant prostate cancer patients²⁹. There is a strong rationale for considering the AR as a therapeutic target in recurrent, non-castrate prostate cancer (BCR).

In the early 1990's, single agent bicalutamide (50 mg daily) was tested as monotherapy in metastatic prostate cancer patients with high PSA levels. By 3 months, 20% of patients had a PSA decline of 85%, and by 6 months, 40% of the patients reached a 90% decline. Those who achieved this response had longer OS; however, this was inferior to complete androgen blockade (castration). Single agent bicalutamide (50 mg daily) was also recently tested as one arm of ECOG 2809 study in patients with BCR and results are pending.

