2.0 OBJECTIVES

2.1 Primary endpoint:

The proportion of patients with undetectable PSA (< 0.2 ng/mL) at 32 weeks with metformin plus bicalutamide compared to bicalutamide monotherapy.

2.2 Secondary endpoints:

- The proportion of patients with PSA decline > 85% at 32 weeks with metformin plus bicalutamide compared to bicalutamide monotherapy.
- The time to PSA progression with metformin plus bicalutamide compared to bicalutamide monotherapy.
- To evaluate the time to onset of radiographic evidence of metastatic disease (rPFS) with metformin plus bicalutamide compared to bicalutamide monotherapy.
- To characterize the PSADT changes pre-study, during treatment, and off treatment.
- To evaluate the safety and tolerability of metformin in this patient population.
- To evaluate QOL with metformin plus bicalutamide compared to bicalutamide monotherapy.
- To evaluate the time to next therapy (i.e. antiandrogen or GnRH antagonist/agonist).

2.3 Exploratory endpoints:

- Immunogenicity of bicalutamide +/- metformin by flow cytometric analysis of T-cell frequency, activation status, cytokine profiles, antibody levels and analysis of sCD27 and sCD40L
- Evaluate circulating PSA levels and correlations with immunogenicity and/ or efficacy

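### Section 11.3 poses a hypothesis about 85% PSA response but tests a split at the pooled median 32-week PSA, so the endpoint has no matching test and the 80% power does not apply to it

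*Combined protocol and SAP*

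**What the plan says.** Section 2.2 lists as its first secondary endpoint "The proportion of patients with PSA decline > 85% at 32 weeks with metformin plus bicalutamide compared to bicalutamide monotherapy".

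Section 11.3 opens with the matching null hypothesis, that "the fraction of arm A and arm B patients with at least 85% reduction in PSA at 32 weeks will be the same". It then describes the analysis: "We will sort the 66 patients 32 week PSAs into groups above or below their grand median 32 week PSA". Next comes "We will then submit the doubly dichotomized data to Fisher's exact test", and the paragraph ends "The test will distinguish an odds ratio of 3.19 from one of 1.0 with 80% power and at most 10% type I error".

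The two dichotomies are therefore arm (A or B) and 32-week PSA (above or below the pooled median). Section 11 gives no other test of the 85% endpoint, no arm A rate for it, and no statement of whether the 10% is one-sided or two-sided.

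**The concern.** The hypothesis concerns a change from each man's own baseline. The test concerns an absolute level at one time point, cut at a value that the pooled data will determine. Section 3.1.9 admits any baseline PSA below 30 ng/mL, so the two can part company. A fall from 25 to 2.5 ng/mL is a 90% decline, yet it can land in the upper half. A fall from 0.6 to 0.3 is a 50% decline, yet it can land in the lower half.

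Followed literally, the first-listed secondary endpoint receives a p-value for another question, together with a power figure that belongs to another test. An analyst who tests 85% responders instead departs from the written plan and loses the stated power. Leaving this open also leaves a choice between two tests that can disagree once data are in hand.

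**Working it through.** **Inputs.** N = 66, randomised 2:1, nominally 44 in arm B and 22 in arm A (section 11.1). Odds ratio (OR) 3.19, power 80%, type I error at most 10% (section 11.3). Sidedness is not stated, so both versions are shown. The arm A rate of 85% response is not given, so it is an assumption shown over a range.

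**Step 1: reproduce the plan's figure.** With no ties, a median split puts 33 men in each half, so all margins of the 2x2 table are fixed. Let X be the number of arm B men in the favourable (lower) half. Under the null, X is hypergeometric (66 men, 44 in arm B, 33 in the lower half). At OR 3.19 it follows Fisher's noncentral hypergeometric distribution.

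- One-sided 10%: reject when X is 25 or more. Size 9.6%, power 82.1%. Exactly 80% would need OR 3.06.
- Two-sided 10%: reject when X is 18 or fewer, or 26 or more. Size 6.6%, power 64.8%.

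The stated 80% is thus consistent with a one-sided median-split test, and no arm A rate is needed because the split fixes the margins. It is not an arithmetic error.

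**Step 2: the same OR on the stated endpoint.** Let pA be the arm A proportion with at least 85% decline, and pB = 3.19·pA / (1 − pA + 3.19·pA). Power is the sum of Binomial(44, pB) × Binomial(22, pA) probabilities over all tables that Fisher's test rejects at 10%.

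| Assumed pA | Implied pB | Power, one-sided | Power, two-sided |
|---|---|---|---|
| 10% | 26.2% | 49.6% | 39.8% |
| 20% | 44.4% | 68.4% | 56.7% |
| 30% | 57.8% | 75.6% | 63.1% |
| 40% | 68.0% | 75.7% | 63.8% |
| 50% | 76.1% | 71.8% | 62.7% |
| 60% | 82.7% | 66.1% | 57.5% |
| 70% | 88.2% | 55.9% | 48.4% |

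On a grid of pA in steps of 0.01, the maximum is 76.3% one-sided (at pA = 35%) and 64.1% two-sided. Reaching 80% needs an OR of at least 3.41 one-sided or 4.14 two-sided at the most favourable pA. At pA = 20% it needs 3.80 or 4.51.

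The documents' only response figures for bicalutamide 50 mg are in section 1.2: "By 3 months, 20% of patients had a PSA decline of 85%, and by 6 months, 40% of the patients reached a 90% decline". Those patients had metastatic disease and the second figure is for a 90% decline, so they are an anchor and no more.

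**Step 3: how far apart the two classifications must be.** If R of the 66 men are 85% responders and 33 are below the median, at least |R − 33| men are classed differently, whatever the PSA distribution.

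- 20% response in both arms: R = 0.20 × 66 = 13.2, so at least 33 − 13.2 = 19.8, about 20 men.
- 40% response in both arms: R = 0.40 × 66 = 26.4, so at least 33 − 26.4 = 6.6, about 7 men.

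**The case against.** Several points on the other side are sound.

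- **Validity under no effect.** If metformin has no effect on PSA, both the 85% fractions and the 32-week PSA distributions are equal between arms, and the median test keeps its size. This stands. The fault is one of relevance and power, not of inflated alpha.
- **The power sentence may describe only the median test.** It follows directly on that test and is right for it if one-sided. On this reading, though, the 85% hypothesis has no test and no power statement at all, and the text still needs repair. The paragraph names no separate hypothesis for a PSA-level comparison.
- **The ceiling below 80% owes something to Fisher's conservatism.** Its largest one-sided size here is only 7.0% at a nominal 10%. Boschloo's exact test at the same sample size, OR and one-sided level gives 75.8% at pA = 20%, 80.9% at 30%, 81.5% at 35%, 81.2% at 40%, 80.5% at 45% and 79.6% at 50%. So the ceiling belongs to Fisher's test, which the plan names, and not to the endpoint as such.
- **The discordance figures are limited.** They rest on assumed rates, the bound is zero at R = 33, and it counts differing labels rather than bias in the comparison of arms. That is a fair limit on step 3.
- **It is a secondary endpoint with no decision rule attached, and the raw PSA values allow the proportions to be tabulated at any time.** True, and this limits the damage. But the plan states a specific test for a specific hypothesis, and the two do not match.

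**Conclusion.** The point holds: section 11.3 is wrong as written. The planned table contains neither baseline PSA nor the 85% threshold, so it cannot estimate or compare the proportions that section 2.2 lists.

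The 80% figure applies to a one-sided median split and does not carry over. With the named test and OR 3.19, the shortfall for 85% responders is at least about 4 points one-sided (80 − 76.3 = 3.7) and 16 points two-sided (80 − 64.1 = 15.9), and larger away from arm A rates near 35%.

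These figures assume a 44/22 split and a 32-week PSA for all 66 men. The arm A rate is an assumption throughout, but the conclusion that Fisher's test falls short of 80% does not depend on which rate is chosen. The primary decision rule, the continuation rule and the sample size in section 11.1 are not touched.

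**What to change.** Rewrite the first paragraph of section 11.3 before the 32-week data are examined by arm:

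1. Define response as the percentage decline from each man's own baseline PSA, and name the baseline reading to be used.
2. Settle one boundary. Section 2.2 uses strictly more than 85%, section 11.3 at least 85%. This will rarely matter but should agree.
3. Apply Fisher's exact test to the 2x2 table of arm by responder status.
4. State sidedness and the assumed arm A rate, and give the power for that rate. With Fisher's test at OR 3.19 it is at most about 76% one-sided or 64% two-sided. If a less conservative exact test is preferred, name it and give its power.
5. If a median test of 32-week PSA is still wanted, list it as a separate analysis with its own hypothesis, sidedness and power statement, and say how values equal to the median are assigned.

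The cost is one paragraph and a less favourable power figure. Table 1 in section 6.1 already schedules PSA at screening, at each cycle and off treatment, so no new data or visits are needed.

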11.0 STATISTICAL CONSIDERATIONS

11.1 Sample size

We will test the hypothesis that only 20% of patients on either arm of the study will have undetectable PSA at 32 weeks, versus the alternative that 40% of arm B patients will. An initial cohort of 39 patients and, if continued, a second cohort of 27 patients will be randomized 2:1 to arms B and A respectively.

After stratification for prior therapy we will randomize, 2:1, nominally 13 patients to arm A and 26 patients to arm B. Because of post stratification randomization, the exact numbers in the two arms may vary slightly from 13 and 26, but the total patient number in the the initial cohort will be exactly 39 and the final sample number be exactly 66. Our intent is to compare the proportions of patients with undetectable PSA at 32 weeks. This is most simply described by the difference $(E1/26) - (C1/13)$, where C1 and E1 are the numbers of undetectable PSAs in arms A and B respectively. The cut point for continuation of the trial past the first cohort requires that

$(E1/26) - (C1/13) > -2/13 = -0.1538462\dots$. To avoid confusion due to round off of such fractions, we identify the decision boundary by $13 E1 - 26 C1 > -52$, exactly equivalent the first expression, and obtained by multiplying all terms by $13*26$.

If $13 E1 - 26 C1$ exceeds -52 AND $E1$ is at least 6 then we will randomize an additional 9 patients to arm A and 18 patients to arm B. Otherwise the study will be terminated and the null hypothesis accepted. Letting $C2$ and $E2$ be the numbers of undetectable PSAs in the second cohort, we will finally reject the null hypothesis if $22(E1 + E2) - 44(C1 + C2)$ is at least 88 and $E1 + E2$ is at least 14. The initial cohort will consist of 39 and the final cohort of 27 patients for a total of 66 patients. If the true null is 20% undetectable PSAs type I error will be 3.24% and power will be 80.3%. In this case the chance of early stopping under the null will be 60% but will be 3.23% if the true arm B fraction of undetectable PSAs is 40%.

If the null (arm A) fraction undetectable PSAs is 25% type I error increases to 10.9% and power increases to 83.3% if the arm B fraction undetectable is 45% (20% higher). If the null fraction is 30% type I error increases to 19.7% and power to 83.2% (arm B 50%, 20% higher).

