The above discussion is based on the exact 2:1 split in the combined strata. This may not occur so the table below describes the decision boundaries for all possible outcomes of the split. In all cases study power is at least 80% and type I error is less than 5%. Type I error when the null fraction is 30% is always under 20%. To use the table we compute $nc1 E1 - ne1 C1$ where $nc1$ and $ne1$ are the actual numbers of arm A and arm B respectively in the initial cohort of 39. If this number, $nc1 E1 - ne1 C1 > -a1$, and $E1 > m1$ in the table, then the trial may be continued past the initial cohort. Otherwise it is terminated and the null hypothesis accepted. If the second cohort is recruited, then $nc2(E1+E2) - ne2(C1+C2)$ must be computed. $nc2$ and $ne2$ are the total numbers of patients in arms A and B respectively. If $nc2(E1+E2) - ne2(C1+C2)$ is at least r and $E1+E2$ is at least $m2$ in the table, then the null hypothesis will be rejected. The table is indexed by $nc1$ and $nc2$ only. This is so because $nc1+ne1 = 39$ invariably as does $nc2+ne2 = 66$. For example, suppose $nc1 = 13$ hence $ne1 = 26$. Then if $E1 = 7$ and $C1 = 4$, $E1 > m1 = 6$ and $13 E1 - 26 C1 = 13 * 7 - 26 * 4 = 91 - 104 = -13$, and $-13 > -52$, so the second cohort would be recruited. Finally, suppose $nc2 = 22$ hence $ne2 = 44$ and suppose $E2 = 9$ and $C2 = 2$. Then $E1+E2 = 9+7=16 > m2=14$ and $22(E1+E2) - 44(C1+C2) = 22*16 - 44*6 = 352-264 = 88$ which is at least $r = 88$. In this case the null hypothesis would be rejected.

decision boundaries						
nc1	nc2	a1	m1	r	m2	
12	21	-42	6	72	14	
12	22	-42	6	88	14	
12	23	-42	6	88	13	
13	21	-52	6	72	14	
13	22	-52	6	88	14	(this row used in example above)
13	23	-52	6	88	13	
14	21	-68	6	72	14	
14	22	-68	6	88	14	
14	23	-68	6	88	13	

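### Randomisation is stratified by prior therapy, but the 11.3 secondary tests pool the strata and no stratified estimate accompanies the primary result; the cost is small unless prior therapy is strongly prognostic.

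*Combined protocol and SAP*

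**What the plan says.** Section 11.1 makes prior therapy a design factor: "After stratification for prior therapy we will randomize, 2:1, nominally 13 patients to arm A and 26 patients to arm B". The levels of the factor are not given there, and section 4.1, on registration and randomisation, does not mention it.

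The primary decision uses counts of men with undetectable PSA pooled over the strata. After the nominal boundaries are set out, the text says "The above discussion is based on the exact 2:1 split in the combined strata" and tabulates boundaries for other splits. The null hypothesis is rejected when 22(E1+E2) − 44(C1+C2) is at least 88 and E1+E2 is at least 14.

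Section 11.3 gives the secondary tests. The 32-week PSA endpoint is a single two-by-two table analysed by Fisher's exact test. For the two time-to-event endpoints, "We will compare arms A and B for each of these end points with log-rank tests". No alpha, event number or power is stated for the log-rank tests, and follow-up is at least 60 months. No stratified or covariate-adjusted analysis appears anywhere in section 11.

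**The concern.** A factor is normally balanced at randomisation because it is expected to predict outcome. If it does, leaving it out of the analysis has two known effects. The pooled test treats variation between strata as noise, although the balanced allocation has already removed it from the arm comparison, so the test falls below its nominal size. For survival data, mixing strata with different hazards also pulls the treatment effect towards the null. Both cost power.

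With 66 men, 22 of them in arm A, the time-to-event comparisons are weak already. Silence on stratification also leaves room to choose between pooled and stratified results once the data are known.

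**Working it through.** **1. Primary rule, as stated.** Inputs from 11.1: cohorts of 39 and 27, nominal arms 13/26 and then 22/44, rates 20% versus 20% (null) and 20% versus 40% (alternative). Trial continues if 13·E1 − 26·C1 > −52 and E1 ≥ 6; final rejection as given above. Exact enumeration of four independent binomials (C1, E1, C2, E2):

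| Quantity | Stated | Recomputed |
|---|---|---|
| Type I error | 3.24% | 3.246% |
| Power | 80.3% | 80.36% |
| Early stopping, null | 60% | 60.05% |
| Early stopping, arm B 40% | 3.23% | 3.236% |

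**2. Primary rule with prognostic strata.** Assume two equal strata, average rates kept at 20% and 40%, and a common odds ratio across strata (400,000 simulations per setting):

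| Arm A rates by stratum | Type I error | Power |
|---|---|---|
| 20/20% | 3.3% | 80.3% |
| 25/15% | 3.1% | 80.6% |
| 30/10% | 2.8% | 82.0% |
| 35/5% | 2.4% | 84.2% |

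Type I error falls and power rises. With 35/5% against 60/20%, exact enumeration gives 83.3% power. The pooled boundary gives nothing away.

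**3. Log-rank tests.** There is no planned figure to reproduce. The unstratified statistic is U²/V, with U = Σ(d₁ − d·n₁/n) and V = Σ d·n₁n₀/n² over event times. The stratified version computes U and V within each stratum and uses (U₁+U₂)²/(V₁+V₂). Assumptions: two equal strata with exact 2:1 allocation in each, treatment hazard ratio 0.5, two-sided 5%. Power, unstratified versus stratified, from two separate simulations:

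| Stratum hazard ratio | About 31 events | About 30 events, stratified test calibrated to a true 5% |
|---|---|---|
| 1 | 51 vs 51% | 48.5 vs 48.1% |
| 1.5 | not run | 47.2 vs 47.2% |
| 2 | 48 vs 50% | 46.5 vs 48.1% |
| 3 | 44 vs 51% | 42.0 vs 48.6% |

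The gain from stratifying at 2 is 50 − 48 = 2 and 48.1 − 46.5 = 1.6 points; at 3 it is 51 − 44 = 7 and 48.6 − 42.0 = 6.6 points. The unstratified size at 3 is 3.5%.

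The event number is also assumed, so it was varied:

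| Stratum hazard ratio | About 18–20 events | About 40 events |
|---|---|---|
| 1 | 34.1 vs 33.9% | 60.0 vs 59.6% |
| 1.5 | 33.9 vs 34.3% | 58.1 vs 58.8% |
| 2 | 33.4 vs 34.8% | 55.2 vs 58.4% |
| 3 | 32.6 vs 36.1% | 48.5 vs 58.4% |

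So the gain at 2 runs from 1.4 to 3.2 points, and at 3 from 3.5 to 9.9 points.

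**4. The primary difference as an estimate.** Take 35/5% in arm A and 60/20% in arm B, with stratum sizes 11/11 and 22/22.

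- Pooled variance: 0.2·0.8/22 + 0.4·0.6/44 = 0.01273, SE 0.113.
- Stratified variance: ¼(0.2275 + 0.0475)/11 + ¼(0.24 + 0.16)/22 = 0.00625 + 0.00455 = 0.01080, SE 0.104.
- Ratio 0.848, about 15% lower.

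With weaker strata, 25/15% and 47.6/32.4%, the stratified variance is ¼(0.1875 + 0.1275)/11 + ¼(0.2494 + 0.2190)/22 = 0.00716 + 0.00532 = 0.01248. The ratio is 0.98, so the saving is only 2%.

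**5. Fisher's test.** The effect of pooling on this test was not computed, so no loss is claimed for it.

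**The case against.** A reader might infer that the primary analysis also wastes power, or that its error rates are wrong because they assume one rate for all men. The documents do not support this. The primary is a fixed count boundary with no standard error in it, the stated figures are for a 20% null and reproduce, and heterogeneity makes the rule slightly safer. A one-sided 5% pooled test compared with a Mantel-Haenszel test at 35/5% versus 60/20% gives 49.7% versus 55.9% power, but the plan uses neither test, so that gap says nothing about the trial's decision.

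A reader might also take it as established that prior therapy is prognostic. Section 3.1.10 sets different failure thresholds after prostatectomy and after radiation, but those are minimum values; 3.1.9 admits any entry PSA below 30 ng/mL in either group. Section 1.2 reports undetectable PSA in 40% to 77% of men on a related regimen according to entry PSA, an odds ratio of (0.77/0.23)/(0.40/0.60) ≈ 5. That is by PSA level, and prior therapy is at most a proxy for it.

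Nor is stratifying costless. With non-prognostic strata, a one-sided 10% test of two proportions has 66.3% power pooled and 65.0% stratified. The number of strata is unknown: 3.1.4 admits surgery, radiation and cryoablation, and 3.1.5 allows prior salvage treatment. Two equal strata leave 11 arm A men in each; three leave about 7. In thin strata the normal reference can mislead: one run with about 30 events and a stratum hazard ratio of 3 gave the stratified log-rank test a size of 6.1%.

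All of this stands as a limit on the point. It does not remove it: the design factor is absent from 11.3 without a reason, and the pooled log-rank test is conservative if that factor matters.

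**Conclusion.** The point holds as an inexpensive improvement to the secondary tests and to the reporting of the primary difference. It is not an error in the plan. With about 30 events and a treatment hazard ratio of 0.5, pooling the log-rank test costs 0 to 1 point of power at a stratum hazard ratio of 1.5 or less, about 2 to 3 points at 2 (nearer 2 at 30 events, 3 at 40) and about 7 points at 3. These figures rest on assumed stratum sizes, prognostic strength and event numbers, none of which the documents give. Pooling makes the tests conservative, so it adds no false-positive risk. The boundary in 11.1, with its stated 3.24% and 80.3%, should be left as it is.

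**What to change.** - In 11.1 and 4.1, define the prior-therapy strata, including where cryoablation and prior salvage treatment belong.
- In 11.3, make the log-rank tests stratified by prior therapy, with p-values from permutation within stratum if strata are thin.
- For the 85% PSA response, use an exact stratified or Cochran-Mantel-Haenszel test.
- Keep the pooled Fisher and log-rank tests as named sensitivity analyses.
- Beside the primary decision, report a Mantel-Haenszel risk difference stratified by prior therapy, with its interval, as an estimate that does not alter the decision.

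The cost is a few sentences of statistical text, settled before outcomes by arm are examined, and no new data. The risk is sparse strata with about 22 men in arm A, and no gain, or about 1 point of power lost, if prior therapy proves not to be prognostic. If the sponsor prefers to pool, a sentence giving the reason would close the point.

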Several retrospective studies demonstrated that early ADT has no significant effect on overall survival (OS) since it decreases prostate cancer-specific mortality (PCSM) but increases non-prostate cancer specific mortality⁸⁻¹⁰. Retrospective study by Garcia-Albeniz and colleagues presented at 2014 Annual ASCO Meeting used the CaPSURE registry to evaluate data from 2,012 patients with PSA-only relapse after radical prostatectomy or radiation therapy. Patients who underwent immediate ADT demonstrated no significant advantage in all-cause mortality (HR=0.94) or prostate cancer-specific mortality (HR=1.15). Estimated 5-year OS rates of 85.1% in the immediate ADT arm and 87.2% in the deferred ADT arm, and estimated 10-year OS was 71.6% in both arms, indicating that there may be no need for immediate ADT treatment in BCR patients¹¹.

Patients with BCR have a variable clinical course: some will have indolent course with no impact their OS; others may have a rapid progression to radiographically apparent metastasis with increased risk for dying from prostate cancer. Comparison of outcomes demonstrated that patients with BCR have a 88% 10-year OS rate in contrast to the 93% 10-year OS rate in men without BCR¹². In a landmark study evaluating BCR following RP, the median time from BCR to clinical progression was noted to be 8 years and from metastasis to PCSM was 5 years¹³, indicating that median OS from the diagnosis of BCR was around 13 years.

PSA doubling time (PSADT) after the prostate cancer treatment can also be used to provide some insight into prognosis. A study of 432 T1-3N0M0 prostate cancer patients who developed BCR following definitive three-dimensional conformal radiotherapy (3DCRT) or intensity modulated radiotherapy (IMRT) from 1989 to 2005 demonstrated that PSADT remains a significant predictor of clinical failure and prostate cancer specific survival. Immediate use of ADT in patients with PSADT of <6 months was significantly associated with improved prostate cancer specific survival, although the survival benefit was less apparent in patients with longer PSADT¹⁴.

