Choueiri and colleagues reported a retrospective analysis of 3,071 men who underwent radical prostatectomy at Duke University (between 1988 and 2008). After a median follow-up of 7.4 years from the time of RP, 17.8 % men had had a BCR and 14.8 % had died of all causes. The median follow-up after PSA failure was 11.2 years. In men who experienced BCR, a PSA doubling time <6 months was associated with a significantly increased risk of overall death from any cause (HR = 1.55)¹⁵.

D'Amico and colleagues have suggested that men who have a BCR with a PSADT > 15 months after RP are at minimal risk for prostate cancer metastasis or prostate cancer specific mortality, whereas those with a PSADT of 3 months or less are at very high risk. Another study of 8,669 patients with prostate cancer treated with RT (5,918 pts) or RP (2,751 pts) found that a PSADT < 3 months was also significantly associated with prostate cancer specific mortality¹⁶.

A retrospective study of patients with BCR who were enrolled in four clinical trials at Johns Hopkins University of the non-hormonal agents: marimastat (a matrix metalloproteinase inhibitor), imatinib, ATN-224 (a copper/zinc-superoxide dismutase inhibitor) and lenalidomide demonstrated that changes in PSADT were prognostic for metastasis-free survival, which may suggest that the onset of metastasis may be delayed if an experimental agent is capable of significantly prolonging the PSADT¹⁷.

In summary, the value of ADT is not clear in BCR population and no study has shown that therapeutic intervention in this setting may improve overall survival. Further research is needed to determine the optimal initiation point of ADT, and whether alternative therapies may delay the need for ADT and prolong survival in this patient population.

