- PSA progression requires a PSA rise above the threshold measured at any time point since the threshold was reached.

3.1.11 PSA doubling time between 3 and 12 months. PSA calculation requires at least two consecutive PSA rises (PSA2 and PSA3) above the threshold PSA (at least 3 PSA values); PSA2 and PSA3 must be obtained within 12 months of study entry. All baseline PSAs should be obtained at the same reference lab. Patient's PSA doubling time must be calculated using the following formula (<http://www.mskcc.org/nomograms/prostate/psa-doubling-time>):

$$\text{PSADT in days} = \frac{0.693 (t)}{\ln (PSA3) - \ln (PSA2)}$$

Where t = the number of days between PSA3 and PSA2

ln = the natural log

PSADT in months = PSADT in days divided by 30.4375

3.1.12 ECOG performance status 0 to 2.

3.1.13 Ability to swallow the study drugs.

3.1.14 Subjects must have normal organ and marrow function as defined below:

- Absolute neutrophil count $\geq 1,000$ /mL
- Hemoglobin ≥ 10 g/dL
- Platelets $\geq 100,000$ /mL
- Total bilirubin within normal institutional limits
- AST(SGOT)/ALT(SGPT) ≤ 1.5 X institutional ULN
- Creatinine clearance ≥ 60 mL/min/1.73 m²
- Hgb A1c $\leq 6.5\%$

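### Section 11.3 leaves entry PSA doubling time out of both time-to-event comparisons, at a modest and conditional cost in precision on secondary endpoints

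*Combined protocol and SAP*

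**What the plan says.** Section 11.3 covers the two time-to-event endpoints in two sentences: "We will characterize the time to PSA progression and the time to onset of metastatic disease using the method of Kaplan and Meier", and then "We will compare arms A and B for each of these end points with log-rank tests". It names no stratum, covariate or regression model, and no alpha, target hazard ratio or event count. Follow-up is to be at least 60 months.

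Elsewhere in the protocol:

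- Section 1.1 reports, from a cohort of 432 men with recurrence after radiotherapy, that "PSADT remains a significant predictor of clinical failure and prostate cancer specific survival". From a prostatectomy cohort it reports that "a PSA doubling time <6 months was associated with a significantly increased risk of overall death from any cause", with a hazard ratio of 1.55.
- Criterion 3.1.11 requires "PSA doubling time between 3 and 12 months" and adds: "Patient's PSA doubling time must be calculated using the following formula". The formula uses two PSA values.
- Section 11.1 stratifies the 2:1 randomisation by prior therapy only. Section 11.3 does not carry that factor into the log-rank tests.
- Sections 2.2 and 7.6 use PSADT as an outcome to be described or explored, not as a baseline covariate.
- Section 4.1 asks for an eligibility checklist at registration. It does not say whether the PSADT value itself is recorded.

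**The concern.** Entry PSADT can vary four-fold within the eligibility window, which straddles the 6-month cut used in section 1.1. The protocol's rationale treats it as prognostic, every enrolled man has a value, and neither the randomisation nor the analysis uses it.

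With nominally 22 men in arm A and 44 in arm B, these comparisons are short of precision. If PSADT is strongly related to outcome, a plain log-rank test gives up power that could be recovered from data already collected. Adjustment is also far more credible if written down beforehand. Added after an imbalance has been seen, it will look selective.

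**Working it through.** **1. The plan's own figures.** Exact binomial enumeration of the two-stage rule in 11.1 (continue if 13E1 − 26C1 > −52 and E1 ≥ 6; reject if 22(E1+E2) − 44(C1+C2) ≥ 88 and E1+E2 ≥ 14) gives:

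- type I error 3.246% (stated 3.24%)
- power 80.36% (stated 80.3%)
- early stopping 60.05% under the null and 3.236% under the alternative (stated 60% and 3.23%)

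The figures reproduce, apart from truncation. They concern the primary endpoint and fix the sample at 66. No power is stated for the log-rank tests.

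**2. Precision of the planned log-rank test.** Assume two-sided 5% and arm HR 0.5. By Schoenfeld's formula at 2:1, power = Φ(|ln HR| × √(2d/9) − 1.96) for d events:

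- d = 20: 0.693 × 2.108 − 1.96 = −0.50, power 31%
- d = 40: 0.693 × 2.981 − 1.96 = 0.11, power 54%
- d = 60: 0.693 × 3.651 − 1.96 = 0.57, power 72%

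Power of 80% needs (1.96 + 0.842)² / (0.2222 × 0.4805) = 73.5, so 74 events, which is more than the 66 patients.

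**3. How far chance imbalance in PSADT can move the estimate.** Assume log2(PSADT) is uniform over 3 to 12 months, a width of 2 doublings.

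- SD = 2/√12 = 0.577
- SE of the arm difference = 0.577 × √(1/22 + 1/44) = 0.151
- 95% range = ±1.96 × 0.151 = ±0.295 doublings
- Factor on the arm HR: 1.5^±0.295 = 0.89 to 1.13, or 2^±0.295 = 0.81 to 1.23, for an assumed HR of 1.5 or 2 per halving
- If the trial stops at 13 v 26 and the HR is 2: SE 0.196, range ±0.384, factor 0.77 to 1.31

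The yardstick is the total uncertainty in the arm HR, exp(1.96/√(2d/9)). That is a factor of 2.53 either way at 20 events, 1.93 at 40 and 1.72 at 59. Dividing (0.151 × ln HR)² by 9/(2d), PSADT imbalance at 22 v 44 makes up about 2%, 3% and 5% of that variance at HR 1.5, and about 5%, 10% and 14% at HR 2.

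**4. Power with and without adjustment.** The simulation used 3,000 trials per scenario, 22 v 44 men, exponential times, 60 months' follow-up, arm HR 0.5 and two-sided 5%. Cells show plain log-rank / Cox adjusted for log PSADT.

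| PSADT HR per halving | about 20 events | about 40 events | about 59 events |
|---|---|---|---|
| 1 (not prognostic) | 37% / 35% | 59% / 58% | 73% / 72% |
| 1.5 | 35% / 33% | 57% / 58% | 71% / 73% |
| 2 | 33% / 32% | 52% / 58% | 64% / 71% |
| 3 | 31% / 33% | 45% / 57% | 53% / 69% |

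With no arm effect, the plain log-rank rejected in 4.4% to 5.7% of trials in every scenario. Prior therapy was not modelled.

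**5. Which column applies to metastasis?** Section 1.1 cites a median of 8 years from recurrence to clinical progression. If times were exponential with that median, the 5-year proportion would be 1 − 2^(−5/8) = 35%, or about 23 of 66 men. The cited cohort was not limited to PSADT of 3 to 12 months and its clock starts at recurrence, so this is only a rough guide. It points to the left-hand column.

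**The case against.** The strongest reply is that the plan contains no error. Under randomisation the unadjusted log-rank test is valid, and chance imbalance in any prognostic factor is already inside its error rate. Step 4 confirms this. A reader might infer that an imbalance in PSADT could pass for a drug effect over and above the stated uncertainty. The documents do not support that: the shifts in step 3 are part of the ordinary sampling error, and a small part at HR 1.5.

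The evidence on PSADT is also indirect. The hazard ratio of 1.55 is for death from any cause after prostatectomy, so it cannot size an effect on PSA progression or metastasis. The sharpest contrast in section 1.1 (above 15 months against 3 months or less) lies largely outside the eligibility window. Nothing in the documents shows that PSADT predicts PSA progression on bicalutamide. A value from two PSA measurements is noisy, which would weaken its effect as a covariate.

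Finally, these are secondary endpoints, Kaplan-Meier with log-rank is conventional, and scans after screening are done only if clinically indicated (Table 1, note 8). Metastasis events may be too few for adjustment to help.

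All of this stands, and it limits the weight of the point. It does not remove the case for pre-specification: the loss if PSADT proves uninformative is about 2 points of power or less, against 6 to 7 points at 40 to 59 events if the HR is 2 per halving.

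**Conclusion.** The point holds as one of precision on two secondary endpoints. Section 11.3 makes no use of a baseline value that the protocol cites as prognostic and calculates for every man.

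At an assumed arm HR of 0.5 and 22 v 44 men, the gain is about 6 to 7 points of power at 40 to 59 events if PSADT has HR 2 per halving. At HR 1.5 the change is about 2 points or less in either direction, and at about 20 events there is essentially no gain. Gains of 12 to 16 points appear only at HR 3 with 40 to 59 events. The arm effect, PSADT effect, PSADT distribution and event counts are all assumed, because the documents give none for these tests.

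Two stronger readings should be resisted. One is that the go/no-go decision or the primary result is affected; section 11.1 rests on the 32-week PSA proportions and does not involve these tests. The other is that adjustment is free; it is cheap, but it has the costs listed with the fix.

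**What to change.** In section 11.3, pre-specify for both endpoints a Cox model of arm with log entry PSADT (the 3.1.11 value) as the single covariate. Stratify it by prior therapy, the randomisation factor, where event numbers allow. Keep the Kaplan-Meier curves and the log-rank test alongside it. State that the numeric PSADT is entered in the study database, not only confirmed as within range.

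The cost is a short change to the SAP, one data field and one model per endpoint. The downsides are one extra parameter, a proportional-hazards assumption, a hazard ratio that is conditional on PSADT rather than marginal, a power loss of about 2 points or less if PSADT is not prognostic, and little benefit for metastasis if events are few.
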